#### Analysis of incidence of TEAE-related variables

- Incidence of skin infection TEAE (excluding herpetic infections) from baseline through week 16
- Incidence of treatment-emergent serious adverse events from baseline through week 16

These endpoints will be analyzed for patient in SAF. The week 16 treatment period is defined in Section 3.2. The Cochran-Mantel-Haenszel test adjusted for randomization strata will be used for the percentage of patients with events described above through week 16.

Multiplicity Considerations

The following multiplicity adjustment approach, a hierarchical procedure, will be used to control the overall Type-I error rate at 0.05 for the primary endpoint and the secondary endpoints across the 2 dupilumab dose regimens versus placebo. Each hypothesis will be formally tested only if the preceding one is significant at the 2-sided 0.05 significance level. The hierarchical testing order is shown in below table (all comparisons are with the placebo).

	Endpoints	Dupilumab	
		Q4W group	Q2W group
Primary endpoint	Proportion of patients with IGA 0 to 1 (on a 5-point scale) at week 16	10	1
Co-primary endpoint for ex-US countries, key secondary for US	Proportion of patients with EASI-75 ( $\geq 75\%$ improvement from baseline) at week 16	9	2
Key Secondary endpoints	Percent change in EASI score from baseline to week 16	11	3
	Percent change from baseline to week 16 in weekly average of daily peak Pruritus NRS	12	4
	Proportion of patients with improvement (reduction) of weekly average of daily peak Pruritus NRS $\geq 3$ from baseline to week 16	13	5
	Proportion of patients with improvement (reduction) of weekly average of daily peak Pruritus NRS $\geq 4$ from baseline to week 16	14	6
Secondary endpoints	Proportion of patients with EASI-50 at week 16	15	7
	Proportion of patients with EASI-90 at week 16	16	8
	Time to onset of effect on pruritus during the 16-week treatment period ( $\geq 3$ point reduction of weekly average of peak Pruritus NRS from baseline)	25	17
	Time to onset of effect on pruritus during the 16-week treatment period ( $\geq 4$ point reduction of weekly average of peak Pruritus NRS from baseline)	26	18
	Change from baseline to week 16 in percent BSA affected by AD	27	19
	Percent change from baseline to week 16 in SCORAD	28	20
	Change from baseline to week 16 in CDLQI	29	21
	Change from baseline to week 16 in POEM	30	22
	Change from baseline to week 16 in weekly average of daily peak Pruritus NRS	31	23
	Percent change from baseline to week 4 in weekly average of daily peak Pruritus	32	24
	Change from baseline to week 16 in HADS	35	33
	Proportion of patients with improvement (reduction) of weekly average of daily peak Pruritus NRS $\geq 4$ from baseline to week 4	36	34
	Incidence of skin-infection TEAEs (excluding herpetic infections) through week 16	39	37
	Incidence of serious TEAEs through week 16	40	38

### 5.7.3. Subgroup Analysis

Subgroup for the primary endpoint and key secondary efficacy will be analyzed based on FAS. The analysis method for the subgroup will be the same as the primary analysis described in Section 5.7.1 and Section 5.7.2. Interactions between the subgroups and treatment groups will also be tested using the logistic regression model for the categorical endpoints, and using the ANCOVA model for the continuous endpoints. The model will include randomization strata, treatment group, subgroup, and treatment by subgroup interaction as factors. P-values for the interaction term will be reported.

Forest plots of the primary and key secondary efficacy endpoints across subgroups will be generated.

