## 5.7. Analyses of Efficacy Variables

For all efficacy variables, the analysis will be comparisons of each dupilumab regimen and the placebo treatment groups. The following null and alternative hypotheses for the primary endpoint will be tested for each dupilumab regimen group and the placebo group:

H0:  $p_{\text{dupilumab}} = p_{\text{placebo}}$  where  $p$  stands for the percent of responders in a treatment group

H1:  $p_{\text{dupilumab}} \neq p_{\text{placebo}}$

The analyses of efficacy variables are described in the subsections below and summarized in [Appendix 10.1](#).

Subgroups are defined by key baseline factors recorded on the CRF and listed to be considered for primary and key secondary efficacy analyses:

- Age group (≥12 to <15, ≥15 to <18)
- Sex (Male, Female)
- Ethnicity: Hispanic or Latino (no/yes)
- Race (White, Black or African American, Asian, Other)
- Duration of AD (< 13 years, ≥13 years)
- Age of disease onset (<2 years, ≥2 years)
- Age of disease onset (<5 years, ≥5 years)

- Family history of atopic disease (Yes/No)
- Baseline weight group (<60 kg, ≥60 kg)
- Baseline BMI group (overweight: ≥ 85 percentile of general population based on age and gender, < 85 percentile)  
Baseline disease severity [moderate (IGA=3) and severe (IGA=4)]
- Baseline severe EASI (<25, ≥25)
- Baseline NRS (<7, ≥7)
- Body Surface Area (BSA) (≥10% - <30%, ≥30% - <50%, ≥50%)
- Previous usage of ciclosporin (CsA) (Yes, No)
- Previous usage of methotrexate (MTX) (Yes, No)
- Previous use of systemic immunosuppressants for AD (Yes, No)
- History of asthma (Yes, No)
- History of allergic rhinitis (Yes, No)
- History of food allergies (Yes, No)

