#### **5.7.2. Analyses of Secondary Efficacy Variables**

The binary secondary efficacy endpoints will be analyzed using the same approaches as that are used for the analysis of the primary endpoints.

The endpoint "Proportion of patients with improvement (reduction) of weekly average of daily peak pruritus NRS  $\geq 4$  from baseline to week 16" will only be analyzed for patients with baseline peak pruritus NRS  $\geq 4$ . Similarly the endpoint "Proportion of patients with improvement (reduction) of weekly average of daily peak pruritus NRS  $\geq 3$  from baseline to week 16" will only be analyzed for patients with baseline peak pruritus NRS  $\geq 3$ .

The continuous endpoints will be analyzed using the multiple imputation (MI) with analysis of covariance (ANCOVA) model as the primary analysis method. Patients' efficacy data through week 16 after the rescue treatment use will be set to missing first, and then be imputed by the multiple imputation method. Missing data from the FAS will be imputed 40 times to generate 40 complete data sets by using the SAS procedure MI following the 2 steps below:

- Step 1: The monotone missing pattern is induced by Markov Chain Monte Carlo (MCMC) method in MI procedure. The monotone missing pattern means that if a patient has missing value for a variable at a visit, then the values at all subsequent visits for the same variable are all missing for the patient.
- Step 2: The missing data at subsequent visits will be imputed using the regression method for the monotone pattern with adjustment for covariates including treatment groups, randomization strata (disease severity, age group), and relevant baseline.

The week 16 data of each of the 40 complete datasets will be analyzed using an analysis of covariance (ANCOVA) model with treatment, randomization strata (disease severity, age group), and relevant baseline included in the model, and the SAS MIANALYZE procedure will be used to generate valid statistical inferences by combining results from the 40 analyses using Rubin's formula.

The imputation model will include:

- The covariates included in the ANCOVA model, including the treatment group, the baseline value and the randomization strata (disease severity, weight group)
- Measured endpoint values at every clinic visit (i.e. week 1, 2, 3, 4, 8, 12 and week 16)

Categorical variables included in above model (i.e., treatment group and randomization strata) are not expected to be missing.

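### The imputation model for the two continuous key secondary endpoints omits the treatment-by-subgroup terms that SAP 5.7.3 tests, so interaction estimates are biased (usually toward zero) and their Rubin standard errors do not match their real spread

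*SAP*

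**What the plan says.** SAP 5.7.2 handles the continuous endpoints by multiple imputation and ANCOVA. Values recorded after rescue are removed: "efficacy data through week 16 after the rescue treatment use will be set to missing first". The gaps are then filled: "Missing data from the FAS will be imputed 40 times to generate 40 complete data sets by using the SAS procedure MI". The imputation model is listed in two items. The first reads: "The covariates included in the ANCOVA model, including the treatment group, the baseline value and the randomization strata (disease severity, weight group". The second adds the endpoint itself over the treatment period: "Measured endpoint values at every clinic visit (i.e. week 1, 2, 3, 4, 8, 12 and week 16".

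The same section is not consistent about the strata. Imputation Step 2 adjusts for "treatment groups, randomization strata (disease severity, age group), and relevant baseline", and the ANCOVA sentence also names age group, while the list above names weight group. SAP 2.1 and Protocol 9.5.2.2 both have weight group.

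SAP 5.7 introduces the subgroups this way: "Subgroups are defined by key baseline factors recorded on the CRF and listed to be considered for primary and key secondary efficacy analyses". Twenty factors follow. SAP 5.7.3 analyses them on the FAS: "The analysis method for the subgroup will be the same as the primary analysis described in Section 5.7.1 and Section 5.7.2". For the interaction test it adds: "The model will include randomization strata, treatment group, subgroup, and treatment by subgroup interaction as factors". Interaction p-values and forest plots are to be reported. SAP Appendix 10.1 confirms subgroup analysis for percent change in EASI and in NRS.

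SAP 5.7.3 does not say which data sets the interaction ANCOVA uses, or whether imputation is run once on the FAS or repeated for each subgroup.

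**The concern.** An imputation model should contain at least the terms that the analysis model estimates. Here the analysis asks whether the treatment effect differs between subgroup levels, but the missing values were filled in from a model with one common treatment effect. Only a patient's own earlier visits can carry subgroup information into the imputed values. Two faults follow: the interaction estimate is biased, and Rubin's variance no longer describes that estimate.

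The question matters in this trial. Protocol 1.2.2 calls weight the main covariate for exposure, and the Q4W arm receives one dose at all weights. A non-significant interaction would be read as evidence of a consistent effect. A test that rejects about 1% of the time under the null gives little such evidence.

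**Working it through.** **1. Terms side by side** (SAP 5.7.2 list against SAP 5.7.3)

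| Term | Imputation model | Interaction ANCOVA |
|---|---|---|
| Treatment, strata | yes | yes |
| Endpoint's own baseline | yes | by reference to 5.7.2 |
| Earlier visits | yes | not applicable |
| Subgroup main effect | severity and weight group, as strata (age group in Step 2's wording); none for most other factors | yes |
| Treatment by subgroup | none | yes |

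Baseline EASI or NRS enters only as the baseline value of its own endpoint.

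**2. The plan's own figures.** The documents give no power, standard error or error rate for interaction tests. The nearest figure is 88% power for IGA 0/1 (29% v 9%, 80 per group, two-sided 0.05; SAP 2.2). Exact Fisher power is 88.1%, so the general inputs reproduce.

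**3. Hand approximation.** Let m_D and m_P be the shares missing at week 16 on dupilumab and placebo, equal across two subgroup levels. Let b be the subgroup difference on placebo and I the true interaction. If earlier visits carried no subgroup information, imputed values within an arm would have the same mean in both levels. The arm's subgroup difference would then shrink to (1 − m) of its true value:

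estimate = (1 − m_D)(b + I) − (1 − m_P)b = (1 − m_D)·I + (m_P − m_D)·b

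The first term is attenuation. The second is a false contribution that appears when the subgroup is prognostic and missingness differs between arms. Worked cases:

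- I = −25, b = 0, m_D = 0.15: 0.85 × (−25) = −21.25
- I = 0, b = 35, m_P = 0.49, m_D = 0.15: 0.34 × 35 = +11.9
- I = −25, b = −20, m_P = 0.50, m_D = 0.15: −21.25 + 0.35 × (−20) = −28.25

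**4. Simulation of the interaction estimate.** Settings: three arms of 80, seven visits, monotone regression imputation with 40 data sets, ANCOVA with interaction, Rubin's rules, 1,000 runs per scenario. Assumed: residual SD 35 points, a 50/50 subgroup, data missing at random given earlier values, visit correlation 0.5 or 0.8 per 4 weeks, and 13% to 70% missing on placebo and 10% to 29% on dupilumab. Monte Carlo error is about 0.3 to 0.5 points on estimates and 0.7 points on a 5% rate. Rows marked * have correlation 0.8.

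| I | b | Missing P / D | Hand | SAP model | Terms added |
|---|---|---|---|---|---|
| −25 | 0 | 14% / 10% * | −22.5 | −23.0 | −24.6 |
| −25 | 0 | about 50% / 15% | −21.25 | −21.7 | −24.9 |
| −25 | 0 | 39% / 28% * | −18.0 | −20.1 | −24.7 |
| 0 | +35 | 49% / 15% | +11.9 | +9.3 | −0.3 |
| 0 | +35 | 67% / 20% * | +16.45 | +11.1 | +0.2 |
| −25 | −20 | 50% / 15% | −28.25 | −28.0 | −25.8 |

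For a non-prognostic subgroup the SAP-model estimate ran from −23.6 to −18.8, a shrinkage of 1 − 23.6/25 = 6% to 1 − 18.8/25 = 25%. In the last row the interaction is enlarged, with median p 0.046 against 0.078 once the terms are added.

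**5. Standard error and rejection with no interaction and b = 0** (all correlation 0.8)

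| Missing P / D | SAP: SD, Rubin SE, reject | Terms added: SD, Rubin SE, reject |
|---|---|---|
| 26% / 10% | 10.75, 11.94, 2.5% | 12.23, 12.12, 5.8% |
| 48% / 15% | 10.04, 12.47, 2.0% | 12.98, 13.23, 5.1% |
| 67% / 20% | 9.38, 13.03, 1.0% | 14.86, 15.16, 4.7% |
| 38% / 29% | 9.85, 12.61, 0.6% | 13.02, 13.20, 4.5% |

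Over all scenarios of this kind, rejection was 0.2% to 3.6%, against about 4% to 6% with the terms added. Rubin's SE exceeded the actual SD in every scenario under the SAP model.

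**6. Other settings.** With 80 per arm, SD 30, a true interaction of 30, 20% / 50% missing (dupilumab / placebo) and rescue at any time after week 1, the SAP model gives 26.2 (hand: 0.8 × 30 = 24). Under the null its Rubin SE is 11.0 against an SD of 8.6, and it rejects 1.4%. With the terms added the figures are 30.0, 11.9 against 11.7, and 5.1%. If data are lost only after week 4, the estimate is 28.5 at 10% / 30% missing (about 5% low) and 26.3 at 20% / 50% (about 12% low).

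**The case against.** Several objections are sound and limit the point.

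- **Direction.** A reader might infer that subgroup differences are always shrunk. They are not: a prognostic subgroup with uneven missingness can produce a false or enlarged interaction.
- **Width.** A reader might infer that the planned error bars are wider than correct ones. They are too wide only for the planned estimator's own spread. Compatible imputation usually gives equal or wider bars (13.4 becomes 14.4 in the 50% / 15% case). Only the interaction term was simulated, so no size is claimed for forest-plot intervals within subgroups.
- **Text.** The SAP does not state that the interaction ANCOVA runs on one FAS-wide imputation. If imputation were repeated within each subgroup, the forest-plot estimates would escape. That is a gap in the SAP, not a wrong method in so many words. Nor are all factors absent: severity and weight group are in as strata, and age group appears in Step 2.
- **Size.** SAP Appendix 10.5 counts topical corticosteroids, tacrolimus and crisaborole automatically as rescue only after day 29. For these the early visits remain, which favours the lower end of the range. Systemic rescue and withdrawal can come earlier.
- **Accuracy.** The biased estimator varies less. In the 50% / 15% case its root mean square error is √(3.3² + 9.1²) ≈ 9.7, against about 13.8 with the terms added. The power gain is modest (30% to 40% there; 65.5% to 70.2% in the step 6 setting with rescue any time after week 1).
- **Consequence.** Only two of the five key secondary endpoints are continuous. The responder endpoints use non-responder rules, not imputation.

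What remains is that a reported p-value should have its stated error rate, and that a reader cannot tell which way a given interaction estimate is wrong.

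**Conclusion.** The point holds as an incompatibility between the imputation model and the interaction model, for percent change in EASI and percent change in peak pruritus NRS, on the natural reading of one FAS-wide imputation. The bias is usually toward zero, about 5% to 25%, but not always in that direction. For a non-prognostic subgroup with no interaction, the test is conservative, mostly rejecting about 1% to 4%. With a strongly prognostic subgroup (+35) and uneven missingness, rejection was about 3% to 6% around a false estimate. These sizes rest on assumed missing shares, residual SD and visit correlation, because the documents give no rescue or dropout rate.

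A reader might also infer that the main results are affected. The documents do not support that: interaction tests do not appear in the hierarchy in SAP 5.7.2, and the main ANCOVA has no subgroup interaction to omit. This is a cheap improvement to a supporting analysis.

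**What to change.** In SAP 5.7.3:

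1. State which imputed data sets the subgroup estimates and the interaction ANCOVA use.
2. For each subgroup analysis of the two continuous key secondary endpoints, re-run the 5.7.2 imputation with that factor and its interaction with treatment added. Where cells are large enough, imputing within treatment-by-subgroup cells is an alternative.
3. Give a rule, fixed before unblinding, for collapsing sparse levels. Race, for example, gives 3 × 4 = 12 cells among 240 patients, 20 on average and probably uneven.
4. Reconcile age group and weight group as the stratum named in 5.7.2.

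The main analysis stays as planned. The cost is SAP wording and up to 20 × 2 = 40 further imputation runs. The interaction estimates will also vary more (SD 13.8 against 9.1 in the 50% / 15% case), usually with somewhat wider standard errors.

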### 9.5.2.2. Secondary Efficacy Analysis

For binary endpoints, the secondary efficacy analysis will use the same approach as that used for the primary analysis.

For continuous endpoints:

- The multiple imputation (MI) with analysis of covariance (ANCOVA) model will be used as the primary analysis method. Patients' efficacy data through week 16 after the rescue treatment use will be set to missing first, and then be imputed by the multiple imputation method. Missing data from the FAS will be imputed 40 times to generate 40 complete data sets by using the SAS procedure MI following the 2 steps below:
  - Step 1: The monotone missing pattern is induced by Markov Chain Monte Carlo (MCMC) method in MI procedure using seed number 12345.
  - Step 2: The missing data at subsequent visits will be imputed using the regression method for the monotone pattern with seed number 54321 and adjustment for covariates including treatment groups, randomization strata (disease severity, weight group), and relevant baseline.

The week 16 data of each of the 40 complete datasets will be analyzed using an analysis of covariance (ANCOVA) model with treatment, randomization strata (disease severity, weight group), and relevant baseline included in the model, and the SAS MIANALYZE procedure will be used to generate valid statistical inferences by combining results from the 40 analyses using Rubin's formula.

- To account for the impact of rescue treatment on the efficacy effect: If a patient receives rescue treatment, the efficacy data collected after rescue treatment is initiated will be treated as missing.
- In addition to the MI method described above, sensitivity analyses such as ANCOVA model with LOCF, MI method with ANCOVA model on all observed data regardless of rescue use will be conducted. Additional details on sensitivity analyses will be provided in the SAP.

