#### Sensitivity analyses

In addition to the MI method described previously, sensitivity analyses for the continuous endpoints for EASI and/or Pruritus NRS will be conducted as described below.

1. The sensitivity analysis based on all observed data regardless if rescue treatment is used or data is collected after withdrawal from study treatment using MI method will be performed.
2. This sensitivity analysis will use ANCOVA model, including the treatment group, the baseline value and the randomization strata. The efficacy data will be set to missing after rescue treatment is used. The post-baseline LOCF method will then be used to impute missing values.
3. This sensitivity analysis will use ANCOVA model, including the treatment group, the baseline value and the randomization strata. The efficacy data will be set to missing after rescue treatment is used. The post-baseline worst observation carried forward (WOCF) method will then be used to impute missing values.

Time to onset of effect on pruritus as measured by proportion of patients with improvement (reduction) of weekly average of daily peak Pruritus NRS  $\geq 4$  from baseline during the 16-week treatment period will be calculated for each patient as (the date of having the first event - the first study drug dose date + 1 day. Patients not having any event during the treatment period will have their time censored at the end of treatment period. Time to onset of effect on pruritus will be analyzed using the Cox proportional hazards model including treatment and randomization strata as factors. The hazards ratio, its 95% confidence interval and p-value will be reported. Kaplan-Meier curves will be provided.

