### 5.12. Analysis of Biomarker Data

Descriptive statistics for the observed values, change from baseline and percent change from baseline values by treatment and visit will be provided for the following biomarker variables:

- TARC
- total serum IgE
- Serum Immunoglobulin profile (IgG/IgM/IgA, IgG subclasses)
- antigen-specific IgE
- Lactate dehydrogenase (LDH)

The Wilcoxon signed-rank test stratified by the baseline disease severity will be used to test if the change or percentage change from baseline value is significantly different from zero. P-value will be reported.

Exploratory analyses for the difference between dupilumab groups and placebo on the change from baseline and percent change from baseline values will be performed using a rank-based ANCOVA model with treatment group and the baseline disease severity as fixed effects, and the relevant baseline values as covariate. Missing value will be imputed by LOCF method for visits between post-baseline to week 16. After week 16, no imputation will be made. P-value for difference from placebo will be provided.

Correlation of baseline TARC (measured value) and IgE (measured value), absolute change or percent change from baseline value of baseline TARC (measured value) and IgE (measured value) with the following clinical endpoints will be explored using the Spearman's rho test. Both Spearman correlation coefficients and p-value will be reported.

- Percent change from baseline to week 16 in EASI score
- Percent change from baseline to week 16 in weekly average of peak daily pruritus NRS
- Change from baseline to week 16 in percent BSA
- Percent change from baseline to week 16 in SCORAD

Correlation of baseline TARC (measured value) and IgE (measured value) with the following clinical endpoints will be explored using the ANOVA model. The model includes the baseline biomarker data as the dependent variable, and treatment group, the responder/nonresponder of below clinical endpoint as the predictor variable. P-value will be provided to indicate significance of the responder/non-responder factor.

- IGA 0-1 at week 16
- EASI-75 at week 16
- improvement (reduction) of weekly average of peak daily pruritus NRS  $\geq 4$  from baseline to week 16

Association of positivity to at least one antigen-specific IgE with the following clinical endpoints will be explored using CMH test stratified by the baseline disease severity. The risk ratio and p-value from the chi squared test will be provided.

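### SAP 5.7.3 does not name the baseline value among the terms of the interaction ANCOVA for continuous key secondary endpoints; the test stays valid, but it may lose some precision for no gain

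*SAP*

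**What the plan says.** SAP 5.7.3 sets out two things. For results within each subgroup it defers to the main methods: "The analysis method for the subgroup will be the same as the primary analysis described in Section 5.7.1 and Section 5.7.2". For the interaction p-values it names logistic regression for categorical endpoints and, for the rest, "using the ANCOVA model for the continuous endpoints". One sentence then gives the terms for both: "The model will include randomization strata, treatment group, subgroup, and treatment by subgroup interaction as factors". Baseline is not mentioned.

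The main ANCOVA for these endpoints does include baseline. Protocol 9.5.2.2 specifies a "model with treatment, randomization strata (disease severity, weight group), and relevant baseline included in the model". SAP 5.7.2 gives the ANCOVA a relevant-baseline term as well, and repeats it in the description of the imputation model: "The covariates included in the ANCOVA model, including the treatment group, the baseline value and the randomization strata (disease severity, weight group"). The LOCF and WOCF sensitivity analyses in SAP 5.7.2 follow suit: "This sensitivity analysis will use ANCOVA model, including the treatment group, the baseline value and the randomization strata".

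The endpoints concerned are the two continuous key secondary endpoints in SAP 4.4.2: percent change to week 16 in EASI and in weekly average of daily peak Pruritus NRS.

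**The concern.** As written, the interaction model for a continuous endpoint contains only categorical terms. That is strictly an ANOVA, although the SAP calls it ANCOVA. Two programmers could reasonably fit different models from the same text, and SAP 5.7 lists about 20 subgroup factors to which it would apply.

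What is at stake is precision in tests that have little to spare. Take one dupilumab arm against placebo at 80 per arm, split into two equal subgroups of 40 per cell. In units of the residual SD, the interaction standard error is sqrt(4/40) = 0.316 and the main-effect standard error is sqrt(2/80) = 0.158, so the interaction is estimated half as precisely. If baseline predicts the endpoint, leaving it out widens the interaction standard error further, and chance baseline imbalance in small subgroups goes unadjusted.

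**Working it through.** **The plan's own figures.** The documents state no power or precision for any interaction test. The stated powers in SAP 2.2 (98, 88, 99, 99, 97 and 95%) concern binary endpoints. Fisher's exact test with 80 per group gives 98.9, 88.1, 99.8, 99.4, 97.7 and 95.9%, so they are sound, but they do not bear on this point.

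**Do the texts differ?** Wherever the documents list the terms of another between-group ANCOVA, baseline appears: protocol 9.5.2.2, SAP 5.7.2 (main model and sensitivity models) and SAP 5.12. SAP 5.7.3 is the exception.

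**Cost of omitting baseline.** With rho the partial correlation of baseline with the endpoint given strata, treatment, subgroup and interaction:

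SE without baseline / SE with baseline = 1/sqrt(1 - rho^2)

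To express this as power, take an interaction with 80% power (2-sided 5%) in the baseline-adjusted model. Its standardized size is 1.960 + 0.842 = 2.802. Without baseline, power is Phi(2.802 × sqrt(1 - rho^2) - 1.960). Rho is not in the documents; the range is assumed.

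| Assumed rho | SE ratio, without/with | Power without baseline |
|---|---|---|
| 0 | 1.000 | 80.0% |
| 0.2 | 1.021 | 78.4% |
| 0.3 | 1.048 | 76.2% |
| 0.4 | 1.091 | 72.8% |
| 0.5 | 1.155 | 68.0% |

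For example, at rho = 0.3: 1/sqrt(0.91) = 1.048; 2.802/1.048 - 1.960 = 0.713; Phi(0.713) = 76.2%.

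**Subgroups cut on the baseline itself.** SAP 5.7 includes bands of baseline EASI (cut at 25) and NRS (cut at 7). The subgroup term then already carries much of the baseline information. As an illustration, assume a normally distributed baseline split at its median. The band explains 2/pi = 0.637 of the baseline variance, leaving 0.363. With r the baseline-endpoint correlation before conditioning on the band:

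rho^2 = 0.363 r^2 / (1 - 0.637 r^2)

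| r | rho^2 given the band | SE larger without baseline, band subgroup | SE larger, subgroup unrelated to baseline |
|---|---|---|---|
| 0.2 | 0.015 | 0.8% | 2.1% |
| 0.3 | 0.035 | 1.8% | 4.8% |
| 0.4 | 0.065 | 3.4% | 9.1% |
| 0.5 | 0.108 | 5.9% | 15.5% |

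Put the other way, adding baseline shrinks the standard error in the band subgroups by 0.7, 1.7, 3.3 and 5.6%.

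**Percent-change endpoints.** Two illustrative EASI models were simulated (3,000 trials each, two arms of 80, binary subgroup, severity and weight strata in the model, assumed distributions). In one, percent change did not depend on baseline, so no gain is possible by construction. In the other, the week 16 score was linear in baseline and then converted to percent change. The SE ratios without/with baseline were 0.997 and 0.999, which is no loss. Type I error was 5.0% without baseline in both models, and 4.9% and 4.8% with it.

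**The case against.** The strongest reply is that baseline is not excluded at all. The sentence in SAP 5.7.3 lists terms as factors and serves the logistic model too; a continuous baseline is a covariate, not a factor. SAP 5.12 draws exactly that distinction, with "treatment group and the baseline disease severity as fixed effects, and the relevant baseline values as covariate". SAP 5.7.3 also speaks of the ANCOVA model just after adopting the methods of 5.7.2, where that model carries baseline. This stands as a plausible reading. A reader might infer that the SAP deliberately removes baseline; the text does not establish that. It leaves the matter open. But the sentence repeats strata and treatment, which 5.7.2 already supplies, so it also reads as a complete list, and the same clarification settles it either way.

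A second reply is that the loss could be nil. This also stands: percent change is already scaled by baseline, the IGA severity stratum is in the model, and nothing in the documents fixes rho.

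A reader might also infer that the omission matters most for subgroups that track severity. The arithmetic shows the reverse for bands of the endpoint's own baseline. IGA 3 versus 4 is itself a stratum, and the documents do not show that duration of AD tracks baseline severity.

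**Conclusion.** The point holds as a small matter of precision and clear specification. SAP 5.7.3 leaves unstated whether the continuous interaction model adjusts for baseline. If it does not, the interaction standard error is between 0% and about 15% larger for an assumed partial correlation of 0 to 0.5, with the lower end quite possible for these endpoints.

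The consequences are limited. Randomization keeps the interaction test valid without baseline, the within-subgroup estimates keep baseline through 5.7.2, and the interaction p-values are not in the testing hierarchy of SAP 5.7.2. No confirmatory conclusion depends on them.

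A reader might expect that adding baseline would bring the interaction p-values into line with the forest plots. It would not, by itself: under 5.7.3 the subgroup estimates come from separate fits, each with its own strata effects and baseline slope, whereas the interaction test is one pooled model. For binary endpoints the SAP likewise pairs CMH results with a logistic interaction test.

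**What to change.** In SAP 5.7.3, after the sentence listing the model terms, add: for continuous endpoints the interaction ANCOVA also includes the relevant baseline value as a covariate; it is fitted to each of the 40 imputed datasets and the results are combined by Rubin's formula, as in Section 5.7.2.

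The cost is one sentence, one model term and one degree of freedom; the data are already collected. The SAP overview allows revision on blinded review before final database lock. The change should also precede any unblinded first-step analysis, since that would be the final analysis of these endpoints.
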